body weight per day, and who are unlikely to tolerate substantial enteral nutrition until several months following their small intestinal insult.

II. Purpose of Study

The specific aim of this study is to ascertain whether PNAC can be reversed if a fish oil-based intravenous lipid product (Omegaven®) at a dose of up to 1 g/kg body weight/day is substituted for a soy-based intravenous lipid product (Liposyn® or Intralipid®) as part of the daily TPN of infants and children with intestinal failure and PNAC. Secondary aims will be to confirm the safety of Omegaven®.

III. Background

In North America, infants and children who require parenteral nutrition (TPN) customarily receive solutions whose caloric distribution is balanced between glucose, protein, and fat to provide approximately 60-70 % of calories via glucose, 10-15 % of calories via protein, and 20-30% of calories via lipid.(1) Commercial lipid solutions utilized in North America are customarily soy-based, and contain high quantities of phytosterols including sitosterol and stigmasterol. Animal data suggest that high quantities of stigmasterol inhibit fxr, a nuclear receptor in the hepatocyte that helps to regulate bile acid homeostasis by controlling expression of bile acid export pumps. (2) Thus, exposure to a high quantity of stigmasterol is potentially hepatotoxic to individuals who have a propensity for cholestasis due to a poorly developed bile secretory process.

It is known that infants and children with underlying intestinal failure are at extraordinarily high risk for cholestasis. (3) The cholestatic process is reversible in approximately ¼ of infants with parenteral nutrition associated cholestasis (PNAC), even when soy-based lipid emulsions are given parenterally, if those infants can experience small intestinal adaptation and ultimately tolerate and assimilate the majority of their calories via enteral nutrition. Unfortunately, if adaptation does not occur rapidly enough, PNAC may progress to endstage liver disease resulting in death or necessitating combined liver/small intestinal transplantation.

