A popular strategy for minimizing the toxicity of lipid emulsions is to reduce the amount of lipid in parenteral nutrition to between 0.5 g/kg body weight/day and 1g/kg body weight/day. (4) Preliminary results suggest that this strategy is beneficial for some infants, but that it is not universally effective. One potential reason for lack of effectiveness among some cholestatic infants is that endotoxemia is commonplace in children with intestinal failure receiving TPN, and that stigmasterol potentiates the cholestatic effect of endotoxin upon the liver. Therefore, when the infant with a cholestatic propensity is exposed to endotoxin and even modest quantities of stigmasterol, cholestasis could progress.

An alternative liver-protective strategy for children on TPN has been to provide all of the patients' parenteral lipid in the form of a fish-oil based product called Omegaven®. (5) This product has been used for over 10 years as an adjunct to conventional fat emulsions.

According to current data, an increase in the proportion of omega-3 fatty acids is thought to optimize nutrition in general, but in particular benefit patients whose underlying disease might benefit from an increase in omega-3 fatty acids. An adequate intake of omega-3 fatty acids results in anti-inflammatory and immunomodulatory effects that are protective against inflammatory tissue damage and capillary permeability. In addition, adults on Omegaven® seem to display improved immunological resistance. Omegaven® may also reduce the risk of thrombosis and increase microvascular perfusion due to its anti-aggregatory and vasodilatory effects.

In Europe and Asia, parenteral omega-3 fatty acids have been used in the following adult patient populations:

1. post traumatic and post surgical patients
2. patients experiencing early stages of sepsis/SIRS
3. patients at risk of hyperinflammatory processes
4. patients with inflammatory bowel disease (Crohn's disease, ulcerative colitis)
5. patients with inflammatory skin diseases (psoriasis, atopic eczema)

The dosing used in these patients was 0.1 (1ml) to a maximum of 0.2 g (2ml) /kg body weight. The infusion rate used did not exceed 0.5ml/kg/body weight/hour. Since it was intended to be infused in combination with conventional fat emulsions, the total fat intake was limited to 10-20% as fish oil. The duration of administration did not exceed 4 weeks.

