While non-North American studies conclude that Omegaven® is safe and that it may have anti-inflammatory properties, they do not address a potential liver protective effect for the agent. Data from North America suggest a salutary role for Omegaven® in PNAC. The group at Boston Children's hospital had initially utilized Omegaven® in a child with soy allergy who required TPN. (8) Subsequently, they reported upon two children who received Omegaven® for PNAC, demonstrating that cholestasis resolved in both and that neither of them experienced side effects. (9). A subsequent open label trial performed at Boston Children's Hospital showed both safety and resolution of cholestasis in 18 children with advanced PNAC.(5) Historical controls receiving soy-based lipid emulsions showed progression of cholestasis rather than resolution. Currently, a double blind, controlled study comparing 1 g/kg body weight/day of Omegaven® with 1 g/kg body weight/day of Intralipid® is being conducted in Boston, and results are quite promising ([name], personal communication). Many other pediatric institutions, including our own, have utilized Omegaven® to treat PNAC. This agent is available in over 30 institutions, and no significant adverse effects have been reported. Small case series and case reports have been published confirming safety and suggesting effectiveness for PNAC (10).

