5. Lack of appetite, nausea, vomiting
6. Dyspnea
7. Headache, pain in the chest, bone pain
8. Priapism
9. Increase/decrease blood pressure
10. Anaphylactic reactions/erythema

Risks for blood draw:

- Occurrence of discomfort and/or a bruise at the site of puncture
- Less commonly, fainting
- The formation of a clot or swelling in the vein and surrounding tissue
- Bleeding from the puncture site
- On rare occasions an infection may develop at the site where the blood is collected

Potential Risks of No Treatment

Since Omegaven® will only be offered to those patients for whom no standard therapy has been safe and effective, the risks of not being treated are those allowing for the natural history of their disease and associated clinical manifestations to progress. These include fulminate liver failure and death.

VII. Overall Risk Assessment

Patients will be at some risk inherent in taking a pharmaceutical agent that has not been fully evaluated for long duration treatment. However, the availability of safety data demonstrates no life-threatening risks or toxicities to vital organs or physiologic functions. The potential benefits of Omegaven® in this patient population are mainly based on human trials and our own experience.

VIII. Risk Category

The research involves greater than minimal risk, but presents the prospect of direct benefit to the individual subjects.

IX. Methods

A. Subject Selection

No concomitant medications will prohibit enrollment.

Inclusion Criteria

1. Males and females ages one month of age to 18 years of age
2. Patients with intestinal failure on TPN
3. Patients who have a conjugated or direct bilirubin of ≥ 3 mg/dl for more than 4 weeks and in whom other causes of cholestasis have been excluded with reasonable certainty utilizing biochemical, serologic, microbiologic, and radiographic techniques. Liver biopsy is not required to rule out other disorders, but may be utilized at the clinician's discretion
4. Patients in whom reduction of IV soy-based lipid load to an **average** <1.2 g/kg body weight/day has failed to reduce the conjugated or direct bilirubin within ≥ 30 days of implementation

5. Willing to use birth control during study participation for females of child-bearing potential, as determined by investigator.
6. Signed informed consent for use of Omegaven® obtained

Exclusion Criteria

1. Any of the contraindications to use of Omegaven®

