Contact will occur by telephone unless subjects are seen in the clinic or are hospitalized. Applicable clinical records obtained at clinic visits and during hospitalizations such as H&Ps, labs, and medications can be used for research purposes.

Treatment with Investigational Drug

For the first two days of treatment, subjects will receive Omegaven® at 0.5 g/kg per day to assess tolerance and will progress to a maintenance dosage range of 0.8 to 1.2 g/kg/day over 12 hours at an infusion rate approximating 1 g/kg/12 hours (10 ml/kg/12 hours). The 12-hour infusion time will be used to minimize waste because of Centers for Disease Control and Prevention requirements that source containers of lipid emulsion be changed every 12 hours. Dosing is based on previously described dosing of fish-oil emulsions as monotherapy noted within the literature (8). Omegaven® will be infused intravenously through either a central or peripheral catheter in conjunction with other parenteral nutrition containing dextrose and amino acids. Omegaven® is isotonic. It is compatible with parenteral nutrition solutions and may be co-infused via y-site.

While hospitalized, serum triglyceride levels will be monitored weekly to insure that triglyceride concentrations do not exceed 1000 mg/dl during the infusion of fat emulsion. During hospitalization, coagulation studies will also be conducted weekly. PT and PTT will be conducted at baseline and then monthly. Other laboratory tests will be conducted to monitor for blood glucose metabolism, electrolyte and fluid balance and liver and kidney function in accordance with current institutional standards for monitoring hyperalimentation. Thromboelastography (prefer with platelet mapping) will be obtained at baseline and approximately 10 days prior to scheduled surgery to assess platelet aggregation dysfunction.

Urine pregnancy tests will be performed at baseline and monthly thereafter for females of child-bearing potential.

The patient will be observed for signs of metabolic overload and other adverse events. Adverse events will be documented by the study staff and may be used as a rationale for dosage adjustments of the study drug.

Study Drug Administration

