The primary endpoint will be reduction in conjugated or direct bilirubin level to below 1 mg/dl. Data from previous retrospective analyses and prospective uncontrolled studies suggest that from the inception of Omegaven® therapy, conjugated or direct bilirubin will remain elevated for approximately 8 weeks at levels comparable to those observed prior to administration of Omegaven®. Subsequently, levels are expected to fall by approximately 1 mg/dl/week until they normalize. The time to normalization will vary according to each patient's baseline conjugated or direct bilirubin level. Thus, a patient who begins Omegaven® with a conjugated or direct bilirubin level of 7 mg/dl is likely to experience normalization within 14 weeks (8+6 weeks). We will compare the group receiving Omegaven® with historical controls from our internal registry who have demonstrated cholestasis while on Intralipid®. We will compare changes in conjugated/direct bilirubin concentration over time between groups via Kaplan-Meier analysis (see Statistics section XIII).

Secondary endpoints will be: normalization of total bilirubin and liver enzymes. Differences in these values at the end of 14 weeks of therapy will be compared with those of controls via Kaplan-Meier analysis identical to that employed for conjugated and direct bilirubin levels. Furthermore, we expect that elevated triglyceride levels which might be present at the initiation of therapy will have normalized at the same time that liver profiles have normalized.

XI. Assessment of Safety/Data Safety Monitoring Board

A DSMB will monitor the study for the occurrence of adverse events (both serious and otherwise). A significant increase in the rate of adverse events would be cause for concern for the safety of participants in the study. Information on adverse events will be presented in several ways: (1) listings of serious adverse events with accompanying narrative summary by the PI; (2) summaries of adverse events by body system and type of event. This information will be presented to the DSMB.

The DSMB will also monitor the efficacy and the conduct of the study. Interim monitoring reports for the DSMB will include, but will not be limited to, such tabulations as:

1. platelet counts
2. essential fatty acid profiles
3. coagulation studies
4. liver profiles

5. renal profiles

The DSMB will meet at least once per year and possibly more frequently given the expected speed of recruitment and study medication administration.

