All adverse events will be followed until they are resolved or the patient's participation in the treatment ends (i.e., until a final report is completed for that patient).

In addition, all SAEs and those non serious events assessed by the Investigator as attributable (i.e. possibly, probably, definitely related to the drug) will continue to be followed even after the patient's participation in the treatment is over. Such events will be followed until they resolve or until the Investigator assesses them as "chronic" or "stable." Resolution of such events is to be documented in the CRF.

XIII. Statistics

We selected a study number of 25 patients (5 patients a year for 5 years) even though, statistically, a number of 19 will be satisfactory based upon power analysis. We know from our current registry that 10% of historic controls will experience resolution of cholestasis within 8 weeks while receiving Intralipid®, and we know from the data of Gura, et al (5) that approximately 50% of experimental subjects will experience resolution of cholestasis within eight weeks while receiving Omegaven®. Thus, achieving an alpha of 0.05 and a beta of 0.80, a sample size of 19 patients and 19 controls will be adequate (11). However, insofar as this is a compassionate release protocol, we will not refuse entry into the study even if we have shown statistically that Omegaven® is efficacious. We estimate that at most we will acquire five patients per year, and we anticipate that within five years, Omegaven® or SMOF (soy, MCT, olive oil and fish oil) parenteral lipids will have obtained FDA approval for clinical use.

The analysis populations will include (1) subjects receiving Omegaven® under this protocol and (2) historical controls from our internal registry who have demonstrated cholestasis while on Intralipid®. Paired t-tests will be used to report the statistical significance of differences between means. A p value of 0.05 or less will be considered significant. Wilcoxon Tests will be used to report the statistical significant differences between medians, and χ^2 tests/Fisher's exact tests will be used to report proportions. A Kaplan-Meier analysis will compare changes in conjugated/direct bilirubin concentration over time between groups. Cox proportional hazard models will be used to estimate crude and adjusted hazard ratios. Analyses will be performed via SAS 9.2 (SAS Institute Inc, Cary, NC) and S-Plus 8.1.1 (Insightful, Inc, Seattle, WA).

IX. Data Management

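### Registry controls have no soy-lipid dose limit and need not have failed lipid reduction, so the comparison may mix lipid type with lipid dose and with refractoriness

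*Combined protocol and SAP*

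**What the plan says.** Section II asks whether cholestasis reverses when Omegaven "at a dose of up to 1 g/kg body weight/day is substituted for a soy-based intravenous lipid product (Liposyn® or Intralipid"®). It gives no dose for the soy lipid being replaced.

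Treated children are tightly defined. Inclusion criterion 4 (Section IX.A) admits only those in whom cutting soy lipid to an average "<1.2 g/kg body weight/day has failed to reduce the conjugated or direct bilirubin within ≥ 30 days of implementation". Criterion 3 adds a conjugated or direct bilirubin of at least 3 mg/dl for more than 4 weeks. After two days at a starting dose they "will progress to a maintenance dosage range of 0.8 to 1.2 g/kg/day over 12 hours" (Section IX.F).

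Controls are loosely defined. Section X says "We will compare the group receiving Omegaven® with historical controls from our internal registry", and Section XIII describes them as "historical controls from our internal registry who have demonstrated cholestasis while on Intralipid"®. Neither section sets a soy-lipid dose, a bilirubin threshold, a prior period of lipid reduction or a start of follow-up. Section XIII plans crude and adjusted Cox hazard ratios but names no covariates.

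The Background (Section III) describes customary parenteral nutrition as giving "10-15 % of calories via protein, and 20-30% of calories via lipid". It also describes a popular strategy, said to benefit some infants though not all, which is to "reduce the amount of lipid in parenteral nutrition to between 0.5 g/kg body weight/day and 1g/kg body weight/day". It cites a controlled study elsewhere "comparing 1 g/kg body weight/day of Omegaven® with 1 g/kg body weight/day of Intralipid"®, in which the dose is held equal.

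**The concern.** The aim is about lipid type. To answer it, the two groups should differ in type and be alike in dose and in response to earlier lipid reduction. The control definition secures neither.

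Two distortions are possible, and they pull in opposite directions. If some controls received more soy lipid than the treated children's lipid dose, a benefit of giving less lipid could be credited to fish oil. If some controls had never tried lipid reduction, they may be easier to reverse than treated children who have already failed it, and Omegaven would look worse than it is. The 10% control rate used for sizing comes from the same registry with no dose or entry condition stated, so the sample size inherits the problem.

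**Working it through.** **1. The two groups side by side.**

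| Feature | Treated | Registry control |
|---|---|---|
| Lipid type during follow-up | Omegaven | Intralipid |
| Lipid dose during follow-up | 0.8 to 1.2 g/kg/day (IX.F) | not stated |
| Failed soy reduction to an average <1.2 g/kg/day | required (criterion 4) | not required |
| Bilirubin ≥3 mg/dl for more than 4 weeks | required (criterion 3) | not required |
| Start of follow-up | start of Omegaven (X) | not stated |

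Only the first row is the question in Section II. The others may also differ.

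**2. How large a dose gap could be.** This needs assumptions that the documents do not supply: 80 to 100 kcal/kg/day in total and 10 kcal per gram of lipid. At 20% to 30% of calories, customary lipid is then 0.20 × 80 / 10 = 1.6 to 0.30 × 100 / 10 = 3.0 g/kg/day. This describes customary feeding, not the registry controls, whose doses are unknown.

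**3. The plan's own sample size.** Inputs from Section XIII: 10% against 50% at 8 weeks, alpha 0.05, and a beta of 0.80 read as power. The cited method is for matched pairs. With 1:1 pairs and no within-pair correlation:
- Odds ratio = (0.5/0.5)/(0.1/0.9) = 9, so P = 9/10 = 0.9.
- Discordant pairs = (1.96/2 + 0.8416 × √(0.9 × 0.1))² / (0.9 − 0.5)² = 9.49.
- Probability that a pair is discordant = 0.5 × 0.9 + 0.5 × 0.1 = 0.50.
- Pairs = 9.49 / 0.50 = 18.99, that is 19.

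The stated 19 and 19 reproduces. There is no arithmetic error; the question is whether 10% is the right control rate.

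**4. Illustration in Omegaven's favour.** Suppose fish oil adds nothing over soy lipid at the same low dose, registry controls resolve at 10%, and treated children resolve at an assumed rate r. Summing the two binomial distributions over every table with two-sided Fisher p ≤ 0.05 favouring Omegaven, 25 against 25:

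| r (assumed) | Chance of a false result favouring Omegaven |
|---|---|
| 10% | 0.4% |
| 15% | 2.8% |
| 20% | 8.5% |
| 25% | 18.0% |
| 30% | 30.5% |

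Fisher's test is one of the planned tests for proportions. Section X's main comparison is Kaplan-Meier, so these figures only indicate scale.

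**5. Illustration for the control rate.** If the control rate is not 10% and Omegaven resolves 50%, the usual two-sided pooled formula without continuity correction gives:

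| Control rate (assumed) | Needed per group | Power with 25 per group |
|---|---|---|
| 10% | 20 | 0.89 |
| 15% | 27 | 0.77 |
| 20% | 39 | 0.61 |
| 25% | 58 | 0.45 |
| 30% | 93 | 0.30 |

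This applies if properly eligible controls resolve more often than 10%. It applies equally if a less refractory registry group does so and hides a real effect.

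**The case against.** The strongest reply is that criterion 4 already deals with dose. Each treated child has had at least 30 days on reduced soy lipid without a fall in bilirubin, and then moves to Omegaven at a similar dose. For that child the switch is mainly one of type, and a dose benefit that did not appear in those 30 days would have to be a delayed one. This stands in part. It makes the higher values of r in the illustration less plausible. It does not limit the controls' dose or history, and the planned comparison is between groups.

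A second reply is that the adjusted Cox model could handle dose. It could, but no covariate is named.

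A reader might infer something stronger: that controls were on high-dose Intralipid, so that the benefit of less lipid will be credited to fish oil and the bias favours Omegaven. The documents do not support that. They give no control doses. The Background calls lipid reduction popular, so many registry children may already have been on it. Parts of the document were not available to this review and could describe the registry. Controls who never failed reduction would bias the result the other way.

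Nor can the Background's figure of about one quarter reversing on soy lipid serve as a low-dose rate. It depends on enteral adaptation and has neither a time frame nor a dose limit. If 25% applied to both groups, the false-positive chance favouring Omegaven would be 1.1% at 25 against 25, not 18.0%.

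**Conclusion.** The concern holds as a possible confounding that the plan does not control. As written, the comparison can mix lipid type with lipid dose and with refractoriness, and so does not isolate the question in Section II. The net direction and size cannot be determined from the documents. The range of 0.4% to 30.5% rests on assumed low-dose rates of 10% to 30%, and criterion 4 makes its upper part less likely. The sample size of 19 and 19 is correct for its inputs. What is uncertain is whether 10% describes children comparable with those treated. The plan should be changed, because the remedy is cheap and the comparison with registry controls is the only between-group evidence on efficacy that the trial will produce.

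**What to change.** In Sections X and XIII:

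- Restrict the primary control group to registry children who meet the trial's clinical entry criteria, including criterion 4: bilirubin not reduced after at least 30 days on average soy lipid below 1.2 g/kg/day. Start their follow-up when those criteria are met.
- Extract soy-lipid dose for controls and lipid dose for treated children. Name dose at time zero as a covariate in the adjusted Cox model.
- As a sensitivity analysis, limit or censor controls by lipid dose during follow-up. This should not be primary: it conditions on exposure after time zero, and the censoring may be informative because dose may follow liver status and feeding.
- Report any comparison with higher-dose controls only as supportive, labelled as a contrast of type plus dose.
- Re-estimate the 10% control rate from the eligible controls and restate power if it changes.

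The Omegaven dose is given as up to 1 g/kg/day in Sections II and IV but as 0.8 to 1.2 g/kg/day in Section IX.F. These passages must be reconciled so that the dose being compared is clear.

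The cost is a wording change, extra registry extraction, fewer eligible controls and possibly a less favourable control rate. The documents do not confirm that the registry holds lipid dose, so this should be checked first. Treatment of enrolled children is unaffected.

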Infants with intestinal failure require chronic administration of parenteral nutrition (TPN). The population under one year of age on TPN is at greatest risk for parenteral nutrition associated cholestasis (PNAC), but, even among older individuals on TPN, the emergence of cholestasis carries a bad prognosis. A number of factors play a role in PNAC. These include endotoxemia, prolonged fasting, immaturity of bile secretory mechanisms among infants, intravenous infusion of high glucose concentrations, intravenous infusion of high protein loads, and intravenous infusions of soy based lipid emulsions. Human data reveal that TPN administered to infants for over three weeks is associated with PNAC. Further analysis reveals that cholestasis is closely associated with the administration of soy-based lipids which contain potentially hepatotoxic phytosterols. Thus lipid reduction strategies have been employed for reversal of PNAC. They sometimes work, but put infants at risk for essential fatty acid deficiency. An alternative strategy of providing lipid in the form of Omegaven®, a fish oil-derived emulsion, is extremely promising, and has been used successfully with virtually no complications in an uncontrolled trial at Boston Children's Hospital. Ongoing controlled studies of Omegaven® are underway at Boston Children's Hospital, and several other institutions have published small case series or case reports suggesting that Omegaven® is effective and safe. It is not FDA approved because none of the ongoing placebo controlled trials have been completed yet in the United States, but, because of its anti-inflammatory properties, it is approved in several European countries for use in adults with inflammatory conditions. Every year, we observe several children in our own practice who have no hope of coming off TPN for several months and who have progressive cholestasis. Our own unpublished data suggest that once PNAC has been established in the absence of endotoxemia, it is usually reversible. However, this may not be true if less than approximately 70% of daily calories are derived enterally. We also have published data in abstract form suggesting that a high conjugated bilirubin to gamma GT ratio is a poor prognostic sign. This study provides Omegaven® for compassionate release to those infants within our practice who have developed progressive cholestasis despite reduction in parenteral lipid below one gram per kilogram

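### The primary comparison with registry controls is an unadjusted Kaplan-Meier analysis; the planned adjusted hazard ratio should be specified for baseline bilirubin and made primary

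*Combined protocol and SAP*

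**What the plan says.** Section X (Assessment of Efficacy) sets the endpoint: "The primary endpoint will be reduction in conjugated or direct bilirubin level to below 1 mg/dl". It then names one method for the comparison: "We will compare changes in conjugated/direct bilirubin concentration over time between groups via Kaplan-Meier analysis", and refers the reader to section XIII (Statistics), which repeats it: "A Kaplan-Meier analysis will compare changes in conjugated/direct bilirubin concentration over time between groups". Neither section mentions stratification, weighting or matching of the two groups.

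Section XIII describes the comparators as "historical controls from our internal registry who have demonstrated cholestasis while on Intralipid". It gives no bilirubin threshold, duration or time zero for them. Treated patients, by contrast, must meet section IX.A: direct or conjugated bilirubin of at least 3 mg/dl for more than 4 weeks, and no fall in bilirubin over at least 30 days of reduced soy lipid.

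On prognosis, section X says: "The time to normalization will vary according to each patient's baseline conjugated or direct bilirubin level". The opening summary adds that established cholestasis is usually reversible without endotoxemia, but that "this may not be true if less than approximately 70% of daily calories are derived enterally". It also calls a high ratio of conjugated bilirubin to gamma-GT a poor sign.

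Directly after the Kaplan-Meier sentence, section XIII adds: "Cox proportional hazard models will be used to estimate crude and adjusted hazard ratios". No covariates are listed, and the plan does not say whether the crude or the adjusted result answers the primary question.

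**The concern.** Without randomization, the two groups can differ at the start in whatever governs time to normalization. The protocol identifies one such determinant, baseline bilirubin, and then names for its primary endpoint a comparison that ignores it. The entry conditions differ between the groups, so there is no reason to expect baseline levels to agree.

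This is the trial's only comparative efficacy result. If controls start higher, Omegaven can look effective when it is not. If treated patients start higher, a real effect can be hidden. Because crude and adjusted hazard ratios sit side by side with no covariates named, the choice between them, and of the adjustment set, could be made after the data are seen.

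**Working it through.** **1. The plan's own figures.** Section XIII assumes 10% resolution in controls and 50% on Omegaven by 8 weeks, alpha 0.05 and power 0.80 (printed as beta), giving 19 per group. For two independent proportions, two-sided, without continuity correction:

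n = [1.96·√(2·0.30·0.70) + 0.842·√(0.10·0.90 + 0.50·0.50)]² / 0.40² = (1.270 + 0.491)² / 0.16 ≈ 19.4, so 20 per group. Power at 19 per group is 79.2%.

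The stated figure is reproduced to within one patient. This two-proportion calculation makes no allowance for baseline differences.

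**2. How strongly baseline matters.** Section X expects about 8 weeks on a plateau after starting Omegaven, then a fall of about 1 mg/dl per week. Time to 1 mg/dl is therefore 8 + (baseline − 1) weeks:

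- baseline 3 mg/dl: 10 weeks
- baseline 7 mg/dl: 14 weeks (the protocol's own example)
- baseline 10 mg/dl: 17 weeks

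Each 1 mg/dl of imbalance shifts the curve by about one week. The protocol gives this trajectory for Omegaven only.

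**3. Illustrative size.** The documents give no baseline distribution for controls, so everything in this step is assumed: no drug effect, 25 per group, mean baseline 7 mg/dl in one group and 7 plus a gap in the other, SD 3 mg/dl, and lognormal noise on the post-plateau time. The ranges cover several simulation set-ups (14- and 26-week horizons, Cox or log-rank test, 150 to 800 runs per cell).

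| Controls higher by | Crude false-positive rate, everyone resolves | Apparent week-14 difference | Crude rate if only 25% ever resolve (log-rank, 14 weeks) |
|---|---|---|---|
| 1 mg/dl | 8-16% | 9-13 points | about 7% |
| 2 mg/dl | 26-41% | 19-20 points | about 9% |
| 3 mg/dl | 49-65% | 28-30 points | about 15% |

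- With treated patients 2 mg/dl higher instead, and everyone resolving, the crude rate is about 25%, now against Omegaven.
- After adjustment for log baseline bilirubin, the error is mostly 7-9%, and 5-12% over all set-ups. It is about 8% even with no imbalance, so the excess over 5% is largely the small-sample behaviour of the test.
- With only 25% resolving and 26 weeks of follow-up, the crude rate is 4-7%. The 25% runs assume that whether a patient ever resolves does not depend on baseline.

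**4. What adjustment cannot do.** A second set of null simulations used a true hazard ratio of 1, an assumed log hazard ratio of −0.5 per SD for bilirubin and for a second, unadjusted factor, and 26 weeks of follow-up.

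| Imbalance | Crude HR | HR adjusted for bilirubin |
|---|---|---|
| Bilirubin only, 0.5 SD | 1.24 | 0.99 |
| Both, 0.5 SD, same direction | 1.53 | 1.26 |
| Second factor only, 0.5 SD | 1.23 | 1.25 |
| Both, 0.5 SD, opposite directions | 1.01 | 1.26 |

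In the second row, the share of bias removed on the log scale is 1 − ln 1.26 / ln 1.53 ≈ 46%. At 25 per group the error there falls from 24% to 12%. In the last row adjustment exposes a bias that had been cancelled by chance.

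**5. How many covariates the data support.** Events by 8 weeks at the planning rates: 25·0.10 + 25·0.50 = 15. Treatment plus three covariates gives 15/4 ≈ 3.8 events per parameter; treatment plus baseline bilirubin gives 15/2 = 7.5. Longer follow-up would add events. The count also rests on the 50% rate at 8 weeks, which does not fit the plateau in section X: from the entry threshold of 3 mg/dl, normalization takes 10 weeks. The two sections need reconciling.

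**The case against.** The strongest reply is that adjustment is already planned: the sentence after the Kaplan-Meier statement promises adjusted hazard ratios. That stands, and a reader who inferred that the plan ignores confounding would be wrong. The gap is narrower. Section X names only the Kaplan-Meier comparison for the primary endpoint, and section XIII neither names covariates nor ranks the results. The sample-size reference is to a paper on matched case-control power, which may mean that matching was intended, but no matching is described.

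The simulated sizes can also be challenged, and much of that challenge holds. The trajectory in section X is given for Omegaven, not for soy lipid. Section III says cholestasis reverses in about a quarter of infants on soy lipid, and section XIII gives 10% at 8 weeks. When only a quarter resolve, most of the inflation disappears. A reader might take a false-positive rate near 60% as the expected error, but the documents do not support that. Nor do they fix a direction: the stricter entry conditions suggest, if anything, that treated patients start higher, which would work against Omegaven.

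A reader might also infer that adjusting for baseline bilirubin removes most of the bias in the historical comparison. The documents contain nothing from which that share could be computed, and step 4 shows it running from all to none or worse. Nor can the covariates be assumed to be in hand. Section IX.F lists a baseline liver profile for treated patients, but no section lists the registry's variables, and enteral share of calories is not a listed data item for either group.

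**Conclusion.** The concern holds in this form: the comparison named for the primary endpoint is unadjusted, the controls are non-randomized and chosen under looser stated criteria, and the protocol itself makes baseline bilirubin a determinant of the outcome. The adjusted Cox analysis that would address this part of the problem is planned, but it is unspecified and not designated as primary.

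The possible distortion runs in either direction. It ranges from small, if few patients ever resolve, to a false-positive rate of roughly 25-40% for a 2 mg/dl imbalance if everyone follows the Omegaven trajectory. These figures rest on an assumed SD, noise and gap, and are illustrations rather than estimates for this trial. Adjustment deals only with bias due to baseline bilirubin. Calendar era, unequal eligibility, an undefined time zero and unmeasured factors remain. The plan should be changed, but the defect is one of specification and does not by itself invalidate the study.

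**What to change.** In sections X and XIII:

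- Make the Cox hazard ratio for time to direct bilirubin below 1 mg/dl, adjusted for baseline direct bilirubin on the log scale, the primary comparison. Present the crude Kaplan-Meier curves as descriptive.
- Put age, enteral share of calories and the ratio of conjugated bilirubin to gamma-GT into sensitivity analyses, where the registry holds them. About 15 events by 8 weeks do not support all of them in the primary model.
- Select controls by the trial's bilirubin and failed-lipid-reduction criteria, with time zero at the date those criteria are met, as far as registry data allow. First confirm which variables and dates the registry contains.
- State that adjustment removes only the bias due to baseline bilirubin, and that residual confounding from calendar era and unmeasured factors remains.

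The cost is SAP wording, one degree of freedom, a check of the registry and possibly fewer eligible controls. No new data are needed from treated patients for the primary model.
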